Please note that all times described in the treatment outline are approximate and if a person cannot attend a scheduled visit we will reschedule it for the next available date.

2) Varenicline Administration. All participants will follow the dose schedule outlined below:

Week 1:

Days 1 to 3: Take 1 x 0.5mg pill each day in the morning.

Days 4 to 7: Take 2 x 0.5mg pills each day. Take one in the morning and one in the evening.

Week 2 to 12:

Take 2 x 1mg pills each day. Take one in the morning and one in the evening.

Participants will be instructed to eat prior to dosing, to take their dose with a full glass of water, and to take doses at least 8hrs apart (please see Appendix 8 for take-home study pill instructions). As noted above, they will receive a 2 week supply of varenicline during their initial interview. They will then receive an additional 1-2 week supply of varenicline on a weekly or bi-weekly basis from weeks 2 to 10.

- 3) Pretreatment preparation visits. Participants will be scheduled for 1 to 3 pretreatment preparation visits with a study therapist. The number of preparation visits will be determined by the study therapist on the basis of the participants assessed level of preparation and motivation to quit smoking. Pretreatment preparation visits will involve motivational interviewing and cognitive behavioral techniques to increase motivation to quit and prepare participants for their quit attempt and treatment.
- 4) Counseling. Throughout the treatment phase, all participants will complete weekly or biweekly counseling sessions with a therapist trained and supervised in smoking-cessation treatment who will review the participant's quit plan (including target quit date and tobacco use reduction plans) and quit status. As part of this assessment participants will complete a Time-Line Follow-back form to assess self-reported smoking behavior since their last treatment visit (see Appendix 4). The study therapist will also administer the Varenicline Toleration Assessment (Appendix 7) during the counseling session, including sessions that occur after the participant has taken their final dose of Varenicline. Counseling will include cognitive-behavioral approaches emphasizing the participant's understanding of the antecedents and consequences of his or her smoking, and

Principal Investigator: [name].

skills training to help the participant cope with situations associated with smoking. Materials that counselors may use during sessions or give to participants as take home materials are listed in Appendix 10. One counseling session, lasting approximately 30 min, will be scheduled weekly or biweekly. Study therapists will receive extensive training and supervision by the study MAI (who may also serve as a therapist as needed).

Date: March 2, 2022

Therapists will either be Masters level counselors or hold a PhD in a relevant field (e.g., psychology) with prior clinical experience. Those with a Master's degree or higher in a relevant field but without clinical experience may also be trained as counselors, but will complete more extensive training that will consist of didactic instruction in principles of cognitive behavioral therapy and cognitive behavioral techniques specific to smoking cessation, observation of counseling sessions with a trained counselor, and observation by a trained counselor of treatment delivery. The MAI and the lead study therapist will meet with all new counselors for an overview of the NRB nicotine cessation counseling program, as well as an in-depth discussion of the theories and techniques behind cognitive-behavioral therapy (CBT) and motivational interviewing (MI). Trainees will also be provided with a manual which outlines the nicotine treatment program, and discusses the MI and CB strategies to be employed at each level of treatment. The individual worksheets and exercises included in this manual will be reviewed with the trainee. New counselors will observe a minimum of 3 treatment sessions, and will be observed a minimum of 3 times by the lead study therapist or [name]. They will also attend the weekly supervision meetings with [name] and the lead study therapist. During the supervision meetings, counselors discuss current cases and bring up any concerns or challenges in order to gain direction and insight in future treatment applications. Bachelor's level staff with a background in psychology or related field may also be trained to fill in for counseling sessions when the primary therapist is not available. They will complete the aforementioned training.

5) Nurse assessment. On the day of their scheduled treatment session participants will meet with a study nurse who will assess their vital signs, and administer an expired CO measurement. CO levels of \geq 4ppm will be considered positive. The study nurse will also administer a urine cotinine test on their first visit after self-reported abstinence and then every 2 to 3 weeks after this, depending on how late in their course of treatment they achieve abstinence. Urine cotinine assessments will only be administered if the participant reports abstinence for the past 7 days \sim 15min.

6) Phone Assessment. During weeks where participants are not scheduled for in-person counseling the study therapist, LI or study clinician will conduct telephone assessments to monitor for changes in physical and psychiatric symptoms (administering the Varenicline Toleration Assessment, Appendix 7) and assess smoking status.

7) Questionnaires. During each weekly visit participants will complete the state measures indicated in Appendix 4. ~15min

(vi) Follow-up.

Participants will be asked to complete follow up visits at 1, 6, and 12 months after their last varenicline dose. During these visits participants will complete a nurse assessment (same as nurse assessment outlined above for scan visits with a definite urine cotinine test), meet with an investigator to assess quit status and

Principal Investigator: [name].

smoking abstinence since last visit, completing state measures indicated in Appendix 4, and complete a 15-20 min scan session involving the following procedures:

Date: March 2, 2022

Structural Images. A set of high resolution structural MR images will be collected. The images will be acquired using a T1-weighed three-dimensional MPRAGE sequence and will be used for the display of functional data. Completion time: ~5 min.

Resting Scan. An EPI scan to assess resting-state fluctuations (RSF) will be conducted. These scans will provide us with information relating to trait and perhaps state connectivity between different prefrontal and limbic brain regions. Completion time: ~10 min.

Heart-rate variability and respiration. Heart-rate variability (HRV) will be measured throughout the two scanning sessions via MRI compatible ECG electrodes placed on the participant's chest or back. Resting HRV provides a trait measure related to enhanced resilience to stress and affect regulation (Friedman and Thayer, 1998; Hansen et al., 2009). Respiration will be measured with a thoracic strain-gauge belt that will be fitted around the individual's waist to control for respiration-related changes HRV. HRV and respiration will be measured during all task and resting functional scans.

(vi)Potential problems and alternatives

1) Missing a treatment visit. If a participant cannot attend their scheduled weekly visit, they will be offered the next available time within that week. If they cannot attend an appointment that week they will be asked to complete their medical monitoring assessment (see Section 8 Subject Monitoring) and counseling over the phone at a convenient time that week.

2) Inability to tolerate varenicline. If participants are unable to tolerate varenicline, they can continue to attend the scheduled counseling visits and assessments and will be offered nicotine replacement therapy (NRT) as an alternative to varenicline treatment. NRT will involve daily application of a dose-matched nicotine patch/patches as well as optional 2 or 4 mg nicotine lozenges. Dose matching will be conducted according to the following schedule of daily patch administration:

10-15 cigarettes per day: 21mg patch 16-20 cigarettes per day: 21mg + 7mg patch

21-25 cigarettes per day: 21 mg + 14 mg patch 26 or more cigarettes per day: 21mg +21mg patch

3) Other issues or concerns expressed by participants regarding the treatment schedule. If any participant expresses concerns or experiences issues regarding attendance at counseling sessions or varenicline administration (e.g., no longer wishes to receive varenicline treatment) we will work with the individual participant to derive a treatment plan that is suitable for them. This will help participants remain in treatment for the full 12-weeks. For example, if any participant wishes to discontinue varenicline treatment but still wishes to attend the counseling sessions, they will be offered NRT as an alternative treatment, but may still continue the counseling sessions in the event that they refuse NRT. Alternatively, if a participant wishes to continue varenicline treatment but has issues/concerns with attendance at counseling sessions, they can continue to receive varenicline treatment without counseling. However, we will require that at a minimum they attend NIDA-IRP at least biweekly to pick up their weeks supply of varenicline, complete a nurse assessment, complete their questionnaires

Principal Investigator: [name].

and receive a brief medical monitoring and abstinence assessment from a study therapist. During the weeks that participants do not come in, study therapists will call participants to conduct telephone assessments to monitor for changes in physical and psychiatric symptoms (administering the varenicline toleration assessment) and assess smoking status.

Date: March 2, 2022

Participants do not wish to attend follow-up visits. If a participant is contacted at the 1, 6 or 12 month follow-up time point and at this point states they do not wish to attend a follow-up visit, they will be asked to complete a part of their follow-up assessment over the phone. The assessment will be conducted by one of the study therapists who will assess the participants quit status and smoking history since their last contact with the study team.

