- Aim 6: To examine the neurobiological basis of motivation to quit smoking and the interaction between motivation to quit and mechanisms underlie acute nicotine withdrawal.
- Q1. Do the self-reported symptoms of acute nicotine withdrawal (e.g., anhedonia, anxiety/irritability, difficulty concentrating, impulsive decision making) and the putative neurobiological processes which underlie these (e.g., enhanced amygdala reactivity, reduced striatal reactivity, hypothesized shift in resting state network dynamics in Fig 1) vary as a function of motivation to quit (treatment-seeking vs non-treatment seeking smokers).
- Q2. Is there a main effect of motivation to smoke (treatment-seeking vs non-treatment seeking smokers) on measures of striatal and amygdala reactivity, cognitive control, drug cue reactivity and resting state network dynamics.

3. Subjects:

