- 4) Nicotine patch toleration test. Participants will complete a nicotine patch toleration test during the orientation visit. Nursing staff will apply the dose-matched nicotine patch at the end of the nurse assessment and will describe potential side effects to the participant. Participants will wear the patch for approximately 3 hours and will be asked to notify the LI or nursing staff immediately if they experience any worrisome side-effects. A nurse will remove the patch and conduct a post patch assessment including vital signs, neck/back pain assessment, mental status exam, and skin assessment.
- 3) Mock scanner training session. The mock scanner training session will familiarize participants with study procedures and the scanner environment. Given that training and scanning will take place on separate days, individuals will receive training refreshers during subsequent visits. ~ 1.5 hrs
- 5) Abstinence period procedure training. Participants will also be trained to measure their CO levels and record this using a small video camera. (see *Abstinence Periods* section for details). At the end of this visit they will generally also receive their first set of nicotine or placebo patches and will be instructed on the application of these during the abstinence periods as well as the time points and procedure for recording their CO and mood/withdrawal symptoms during their upcoming abstinence period. Subjects will also be provided with written instructions on how to apply each patch (see Appendix 5). CO monitors and video cameras and paper copies of self-report measures to complete during the abstinence period will also be distributed to participants at the end of their orientation session. Participants will also be provided instruction in cognitive behavioral techniques (e.g., progressive relaxation) designed to reduce withdrawal discomfort and improve compliance to the 36 hour abstinence procedure ~40min
- 6) Assessment of motivation and preparation to quit. Several measures assessing participant motivation and preparation to quit smoking (see Appendix 9) will be administered to the treatment-seeking smokers and those who enroll in the motivational arm. ~20min

Principal Investigator: [name].

(ii) Abstinence periods

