Go/No-go Task: Inhibitory control processes - cognitive context. Participants will perform multiple blocks of a Go-NoGo task designed to study the ERP and fMRI correlates of response inhibition, error detection and post-error behavioral adjustments. The goal of the go-nogo task is to press a button following each target stimulus (go-trial) and to withhold a response following each lure stimulus (NoGo-trial). In each block of the task participants will view a serial stream of alternating Xs and Ys. Participants will be instructed to make a righthanded button press response to each target stimulus (an X or Y that is different from the last X or Y stimuli presented) while the stimulus is still on the screen. In contrast, responses will need to be inhibited following lure stimuli, defined as a non-alternating target stimulus (i.e., the second of two consecutively presented identical stimuli such as XX). Within each block, most of the stimuli will be targets, while only a small portion will be lures. Task blocks will be interspersed with resting fixation blocks which will be employed as a baseline for some analyses. Performance on this task is quantified as the number of successful inhibitions that participants are able to achieve. Stimulus duration on this task will be individually tailored to produce an equivalent number of successful inhibitions and commission errors across participants. Specifically, during training in the mock scanner environment an appropriate difficulty-level will be selected. The combination of shorter stimulus durations and the instruction to respond while the stimulus is on-screen, yields increased numbers of commission errors (Garavan et al., 2002). Robust differences in brain activity and behavioral performance have been observed using this paradigm to study cocaine addicts (Kaufman et al., 2003). Completion time: ~20 min.

7) Break. Following completion of the AM-session, participants will take a break. Prior to the break laboratory technicians will remove the EEG cap from their head and allow the participants to wash and dry their

Principal Investigator: [name].

hair. During the break time participants will be able to have lunch, relax, and spend time in the day room at their leisure. The break will last \sim 60 min.

Date: March 2, 2022

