10.1. Primary outcomes measures

1) Change in BOLD signal and FC related to task parameters, between drug conditions: will provide important insight into the neurobiological mechanisms underlying acute nicotine withdrawal, in particular those related to anhedonia, negative affect, inhibitory control and impulsive decision making.

Date: March 2, 2022

- 2) Behavioral performance on each of the tasks assessing inhibitory control processes, reward responsiveness, amygdala, striatal, BNST reactivity and impulsive decision making (e.g., reaction time, error rate, hit rate, reward bias): will provide task-related parameters necessary for analysis of BOLD data. Performance data will function as a secondary outcome by providing behavioral validation of acute nicotine withdrawal effects.
- 3) Self-reported craving, withdrawal symptoms and mood/affect: will be employed as regressors in the analysis of task and resting BOLD data. They will also provide the primary means of validating the acute nicotine withdrawal manipulation.
- 4) Smoking status at 1, 6 and 12 months: Smoking status (relapse vs abstinent) at each of the follow-up time points will be based on 7-day point prevalence defined as no smoking (not even a puff) or use of any tobacco products for the past 7 days. This is a standard method of assessing abstinence and dichotomizing relapse status at follow-up (Keating & Siddiqui, 2006; Leventhal et al., 2008; Swan et al., 2010b). Whenever abstinence at follow-up is assessed in-person, self-reported abstinence will be corroborated with breath CO and urine cotinine levels.

10.2. Secondary outcome measures include:

- 4) MRS for glutamate concentration: Glutamate concentration at the PFC and hippocampus is expected to change as a function of acute nicotine withdrawal and may also play a role in the expected reduction in VS reactivity and anhedonia.
- 5) Plasma ACTH and cortisol: are expected to increase as a function of acute nicotine withdrawal and is expected to play role in both anhedonia and negative affective symptoms, potentially by acting at the amygdala, BNST and VS.
- 6) Resting state CBF from ASL: To test for changes in neural activity (i.e., not connectivity) at rest it is necessary to employ a measure which does not require a baseline. CBF provides such a measure as changes in blood flow are referenced to a common arterial location outside of the brain.

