RSN dynamics under acute nicotine withdrawal. The presence of three independent RSNs resembling the ECN, DMN and SN will be confirmed by applying an Independent Component Analysis (ICA) to the band pass filtered (0.01 to 0.08 Hz) resting BOLD time-series. ICA analysis will be conducted using the FSL Melodic ICA software (http://www.fmrib.ox.ac.uk/analysis/research/melodic/). The time-series of six seed regions reflecting core-nodes within each of these networks (ECN: dlPFC, PPC; DMN: vmPFC, PCC; SN: dACC, anterior insula) will then be regressed against each other to assess within and between network rsFC. Fisher r to z transformations will be applied to assess changes in rsFC between nicotine-deprived and non-deprived conditions. Bivariate partial correlations (controlling for nicotine dose) will also be conducted between the degree of change in rsFC within/between the three networks and changes in self-reported affective/cognitive withdrawal symptoms/urge to smoke as well as changes in working memory and attention indices. Treatment seeking status (Treatment seeking vs non-treatment seeking) will be included as a between-subjects factor in these models to assess the main effects and of motivation to quit as well as any interaction between motivation to quit and acute nicotine withdrawal. Correlations will be conducted separately for non-treatment and treatment seeking groups.

Principal Investigator: [name].

Relapse vs non-relapse group comparisons. Neurobiological processes underlying acute nicotine withdrawal will be assessed as a function of relapse status at each of the follow-up time-points by conducting between group comparisons.

Date: March 2, 2022

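### Go/No-go stimulus duration is tuned to equalise successful inhibitions across participants, so the treatment-seeking main effect on that count says little about stable differences in inhibitory control

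*Combined protocol and SAP*

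**What the plan says.** The Go/No-go description in Section 4.4 defines the score: "Performance on this task is quantified as the number of successful inhibitions that participants are able to achieve". It then says: "Stimulus duration on this task will be individually tailored to produce an equivalent number of successful inhibitions and commission errors across participants". As to timing, "during training in the mock scanner environment an appropriate difficulty-level will be selected". The orientation procedures add: "Given that training and scanning will take place on separate days, individuals will receive training refreshers during subsequent visits". No later re-tuning is described. The text also does not say that the duration is locked once chosen.

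Four places bear on how the score is used:

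- Section 2.3, Aim 3 lists go-nogo behavior among its measures.
- Section 2.3, Aim 6 Q2 asks for a main effect of treatment-seeking status "on measures of striatal and amygdala reactivity, cognitive control, drug cue reactivity and resting state network dynamics".
- Section 10.1 lists as primary outcome 2 "Behavioral performance on each of the tasks assessing inhibitory control processes, reward responsiveness, amygdala, striatal, BNST reactivity and impulsive decision making". The same item also says: "Performance data will function as a secondary outcome by providing behavioral validation of acute nicotine withdrawal effects".
- Section 11.2 enters behavioral measures into repeated-measures models with deprivation as the within-subject factor and treatment-seeking status as the between-subject factor, to assess the group main effect and the interaction.

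No section names the tuned stimulus duration as an outcome, a covariate or a recorded variable.

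**The concern.** The quantity that defines performance is the quantity the tuning is meant to make equal across people. If tuning succeeds, two smokers with different inhibitory control produce similar counts at different durations, and the difference between them sits in the duration. A group comparison of the count then has little left to detect. A null treatment-seeking main effect could be read as no difference in cognitive control when the task was set up to give that result.

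There is a second, smaller consequence. If the groups differ in ability, they are scanned at different stimulus durations. Between-group BOLD and ERP contrasts on this task then mix group with stimulus timing, and no analysis examines that.

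**Working it through.** **1. The plan's own figures.** Section 11.4 gives no power calculation for a group main effect on a behavioral count. Its nearest two-group figure is for relapse: d = 0.65, one-tailed α = 0.05, power 0.80, about 30 per group. With the noncentral t, δ = 0.65 × √(30/2) = 2.517, df = 58, critical t = 1.672 and power 0.800. The figure reproduces, and tailoring does not enter it. The within-subject figure (d = 0.5, r = 0.5, power 0.80, about 35) also reproduces: a paired t-test needs 34.

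**2. Group main effect on the count.** Inputs from the documents: 85 treatment-seeking and 35 non-treatment-seeking completers (Section 11.5) and α = 0.05 (Section 11.3). Assumptions: a two-sided test, a true stable difference of d = 0.5 on untuned counts, and a fraction f of it removed by tuning. The documents give neither d for this comparison nor f; their stated aim of equivalence points to a high f.

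δ = d(1 − f) × √(85 × 35 / 120) = d(1 − f) × 4.979, df = 118, critical t = 1.980.

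| f | remaining d | δ | power |
|---|---|---|---|
| 0 | 0.50 | 2.490 | 0.69 (0.695) |
| 50% | 0.25 | 1.245 | 0.23 (0.235) |
| 80% | 0.10 | 0.498 | 0.08 |
| 90% | 0.05 | 0.249 | 0.06 |
| 100% | 0 | 0 | 0.05 |

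With d = 0.65 instead, power is 0.89 at f = 0, 0.36 at 50%, 0.06 at 90% and 0.05 at 100%.

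**3. What tuning leaves intact.** Inhibition counts were simulated on the logit scale for 35 versus 85 participants. All settings are assumptions: 60 lures per session, ability SD 1, withdrawal effect mean 0.4 and SD 0.5, session noise 0.3, duration set once from 20 to 100 training lures, two-sided 0.05.

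- Groups differ only in stable ability (d = 0.65): power on the level of the count falls from 0.85 untuned to about 0.05 tuned.
- Groups differ only in withdrawal response (d = 0.65): power on the deprived-minus-non-deprived change is 0.49 untuned and about 0.54 tuned. Power on the level in the deprived session rises from 0.26 to between 0.48 and 0.59.
- The within-person deprivation contrast has power of at least 0.985 in every scenario.

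A single setting made before both scans therefore removes stable differences from the level and leaves change, and group differences in change, detectable. If the duration were re-tuned at each visit, the change would be lost as well. The text neither describes nor excludes that.

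**The case against.** The tuning has a purpose. The task is meant to study neural correlates of inhibition, errors and post-error adjustment, which needs enough of both trial types from every participant; Section 8.10 also links individual difficulty adjustment to keeping participants engaged. Section 10.1 gives performance a validating, secondary role, which is the within-person use that tuning leaves sound. Aim 6 Q2 is an open question about cognitive control in general, and response-time variability, BOLD, ERP and the separate sustained-attention task are not equalised by the tuning target. All of this stands. It lowers the stakes and is a reason to keep the tailoring, but it does not withdraw the group main effect that Section 11.2 plans for behavioral measures.

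Two stronger readings are tempting, and the documents support neither.

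- A reader might infer that the relapse comparison is also nullified, since Section 11.2 carries it out "by conducting between group comparisons". But the subject of that sentence is the neurobiological processes of withdrawal, and Section 11.4 bases d = 0.65 and the directional hypotheses on neurobiological measures and withdrawal-related changes. Nothing enters the level of the Go/No-go count there.
- A reader might infer that every between-group comparison on this task is lost and only the within-person contrast survives. Because difficulty is chosen in training before both scans, the group-by-deprivation interaction and any group comparison of withdrawal-induced change also survive.

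**Conclusion.** The point holds for one planned inference: the treatment-seeking main effect on the Go/No-go inhibition count, and likewise on commission errors, read as evidence about stable inhibitory control. For that use the count is close to uninformative by design. The size depends on two assumptions that the documents do not supply, the true difference and the share removed. At d = 0.5, power is about 0.24 if half is removed and 0.05 to 0.08 if 80% or more is removed, against about 0.70 untuned. The direction follows from the protocol's stated aim of equivalence; the exact loss does not.

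The deprivation contrast, its interaction with treatment-seeking status and comparisons of change remain interpretable, on the condition that the duration is the same at both scans. This should be corrected before analysis, but it does not threaten the trial's main within-person question.

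**What to change.** Keep the individual tailoring, and add the following to Sections 4.4 and 11.2:

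1. The stimulus duration selected in training is recorded and held fixed across both scan visits.
2. Inference on inhibition and error counts is limited to within-person change and its interactions. A group main effect on the counts is not interpreted as a difference in cognitive control.
3. The tuned stimulus duration is the Go/No-go between-group behavioral measure for Aim 6 Q2.
4. Between-group BOLD and ERP contrasts on this task are reported with and without duration as a covariate, as a sensitivity analysis. Duration should not be a routine adjustment, since it may carry part of a true group difference.

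The cost is small: the value is already set for each participant, so the work is recording it, some wording and one extra analysis. The downside is that duration is a coarser measure, taken from a single training session.
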